## 4 Sample Size

For the primary endpoint, the required sample size was set by first setting the threshold value for assessment of efficacy, and then using binomial distribution to determine the number of subjects required to maintain a 90% or higher probability that the lower limit of the 95% confidence interval (CI) for the percentage of subjects achieving the primary endpoint will be above the threshold value.

As reference information for the threshold value and binomial distribution parameter required to set the sample size for the trial, a threshold of 0.3 and a binomial distribution parameter of 0.5 to 0.6 were used based on interviews with clinicians, since no clinical trial results for administration of tolvaptan in pediatric patients have been obtained either in Japan or other countries.

Based on the above, the required number of subjects was calculated to be a minimum of 68 for a parameter of 0.5 and a minimum of 30 for a parameter of 0.6.

A sample size of 30 to 68 subjects was therefore considered to be appropriate, and in view of feasibility the number of subjects for the trial was set at 60.

## 5 Statistical Analysis Datasets

### 5.1 Full Analysis Set (FAS)

The full analysis set (FAS) includes all subjects who received at least 1 dose of the IMP and have postdose data on body weight and daily urine volume.

### 5.2 Dose Maintenance Analysis Set

The dose maintenance analysis set includes all subjects who received administration at same dose for at least 3 days in the full analysis set.

### 5.3 Safety Analysis Set (SAS)

The safety analysis set (SAS) includes all subjects who received at least 1 dose of the IMP.

### 5.4 Pharmacokinetic Analysis Set

The pharmacokinetic analysis set includes all subjects who received at least 1 dose of the IMP and have postdose data on drug concentration.

## **5.5 Pharmacodynamic Analysis Set**

The pharmacodynamic analysis set includes all subjects who received at least 1 dose of the IMP and have postdose pharmacodynamic data.

## **5.6 Handling of Missing Data**

If data on body weight and edematous symptoms cannot be obtained for assessment on (the day after) the third day of administration at the evaluation dose, the missing data will be imputed using the last available data obtained by that day.

If data on body weight on the day after the third day of administration at the evaluation dose cannot be obtained for the primary endpoint, the definition of the primary endpoint, “the mean daily urine volume for the 3 days of treatment at the evaluation dose” ([Section 6.1](#)), will be changed to “the mean daily urine volume from the start of administration at the evaluation dose to the day on which the imputed data on body weight is obtained.”

If data on body weight, edematous symptoms, and safety endpoints cannot be obtained even on the day of (or the day after) the final administration at the evaluation dose and the day of (or the day after) the final administration, the missing data will be imputed using the last previous data obtained.

The missing data will be imputed when there are data after the administration at the evaluation dose for (the day after) the third day of administration at the evaluation dose and the day of (or the day after) the final administration at the evaluation dose, or after the IMP administration for the day of (or the day after) the final administration (‘after the administration at the evaluation dose’ for the analysis with baseline as the first day or immediately before the start of administration at the evaluation dose).

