3.10 Definition of Completed Subjects

Subjects who have received IMP administration at evaluation dose (see [Section 7.4](#)) for 3 days will be defined as trial completers.

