4.2 Restricted Concomitant Medications

The dose and regimen of the following medications should not be changed from the pretreatment observation period through the completion of an examination 2 days after final administration in principle. Change of dose and regimen during this period is allowed if it is required for safety reasons. In such cases, “the reason of change” and “the details of change” should be recorded. Within 24 hours before and after first tolvaptan administration, however, the dose and regimen of restricted concomitant medications should not be changed (if changed, the subject’s participation in the trial should be discontinued).

- Therapeutic drugs for heart failure (injectables): Catecholamine preparations, human atrial natriuretic peptide preparations, phosphodiesterase 3 inhibitors, colforsin preparations, etc
- Diuretics (oral preparations and injectables)

5 Reporting of Adverse Events

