## **5.7 Definition of Evaluation Dose**

Of the doses administered as specified in [Section 3.2.2](#) and [Section 3.2.3](#), the dose meeting the following criteria is defined as an evaluation dose.

- 1) If sufficient increase in urine volume was obtained during the course of dose escalation, or if the dose was increased to 0.5 mg/kg/day because sufficient increase in urine volume was not obtained:
  - If the dose was not subsequently reduced, then that dose
  - If the dose was reduced without having been administered for 3 days, then the reduced dose
  - If the dose was reduced after having been administered for 3 days, then the dose before reduction

- 2) If IMP administration was discontinued before sufficient increase in urine volume was obtained during the course of dose increase:
  - The dose at final IMP administration

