## 7.5            Prior and Concomitant Medications

For the full analysis set and safety analysis set, frequency distributions for usage of concomitant medication on the initial IMP administration day will be calculated.

Table 7.5-1      Usage of Concomitant Medication on the Initial IMP Administration Day	
Variable	Level
Category of diuretic *Concomitant use of diuretic drugs other than loop diuretic, thiazide diuretic, and anti-aldosterone drug is not summarized.	Monotherapy with loop diuretic, Loop diuretic + thiazide diuretic, Loop diuretic + anti-aldosterone drug, Loop diuretic + thiazide diuretic + anti-aldosterone drug
Thiazide diuretic	No, Yes
Anti-aldosterone drug	No, Yes
Drugs for heart failure other than diuretics	No, Yes
CYP3A4 inducers	No, Yes
CYP3A4 inhibitors	No, Yes

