# 8      Efficacy Analysis

The following analyses will be performed in the full analysis set and the dose maintenance analysis set.

Efficacy will be comprehensively assessed based on the results of primary and other endpoints.

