**Appendix 1****List of Summary Tables**

- CT-1.1 Subject Disposition (Screened Subjects)
- CT-1.2 Analysis Set (IMP Administered Subjects)
- CT-2.1 Protocol Deviations (IMP Administered Subjects)
- CT-2.2 Reasons for Discontinuation (IMP Administered Subjects)
- CT-3.1.1 Demographic and Baseline Characteristics (Full Analysis Set)
- CT-3.1.2 Demographic and Baseline Characteristics (Safety Analysis Set)
- CT-3.2.1 Baseline Disease Evaluation (Full Analysis Set)
- CT-3.2.2 Baseline Disease Evaluation (Safety Analysis Set)
- CT-4.1 Concomitant Medications Used on the First Day of Trial Drug Administration (Full Analysis Set)
- CT-4.2 Concomitant Medications Used on the First Day of Trial Drug Administration (Safety Analysis Set)
- CT-5.1.1 The percentage of subjects who decreased their body weights by 1.7% or more from baseline under conditions of increased daily urine volume (Full Analysis Set)
- CT-5.1.2 The percentage of subjects who decreased their body weights by 1.7% or more from baseline under conditions of increased daily urine volume (Dose Maintenance Set)
- CT-5.1.3 The percentage of subjects who decreased their body weights by 1.7% or more from baseline under conditions of increased daily urine volume by Age Category (Full Analysis Set)
- CT-5.1.4 The percentage of subjects who decreased their body weights by 1.7% or more from baseline under conditions of increased daily urine volume by Age Category (Dose Maintenance Set)
- CT-5.1.5 The percentage of subjects who decreased their body weights by 1.7% or more from baseline under conditions of increased daily urine volume by Evaluation Dose (Full Analysis Set)
- CT-5.1.6 The percentage of subjects who decreased their body weights by 1.7% or more from baseline under conditions of increased daily urine volume by Evaluation Dose (Dose Maintenance Set)

- CT-5.1.7 The percentage of subjects who decreased their body weights by 1.7% or more from baseline under conditions of increased daily urine volume by Evaluation Dose by Age Category (Full Analysis Set)
- CT-5.1.8 The percentage of subjects who decreased their body weights by 1.7% or more from baseline under conditions of increased daily urine volume by Evaluation Dose by Age Category (Dose Maintenance Set)
- CT-5.2.1 The percentage of subjects who decreased their body weights by 1.7% or more under conditions of increased daily urine volume with Start Day of Evaluation Dose as Baseline (Full Analysis Set)

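### No planned analysis counts early stopping, or a started or increased diuretic or injectable heart-failure drug, as non-response; one supplementary responder table would fill the gap

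*SAP*

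**What the plan says.** **Early stoppers.** The primary endpoint is a weight loss of at least 1.7% on the day after the third day at the evaluation dose, with mean daily urine volume above the pretreatment value (Protocol 3.5.1, SAP 6.1). If that weight is missing, "the missing data will be imputed using the last available data obtained by that day" (SAP 5.6, also Protocol 7.3), provided there are data after dosing at the evaluation dose. The full analysis set (FAS) keeps any treated child with postdose weight and urine data (SAP 5.1).

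**Second efficacy set.** Efficacy analyses are "performed in the full analysis set and the dose maintenance analysis set" (SAP 8). The dose maintenance set "includes all subjects who received administration at same dose for at least 3 days in the full analysis set" (SAP 5.2). The responder tables in SAP Appendix 1 (CT-5.1.x, CT-5.2.x) vary the set, age group, evaluation dose or baseline, and SAP 8.1.1 adds other time points. None counts stopping or an added drug as failure.

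**Concomitant drugs.** Protocol 4.2 asks that diuretics and injectable heart-failure drugs stay unchanged in principle, then adds: "Change of dose and regimen during this period is allowed if it is required for safety reasons". Only a change within 24 hours either side of the first dose ends participation. The section speaks of changed dose and regimen and does not name newly started drugs. The reason and details of a change are recorded. In the SAP, "frequency distributions for usage of concomitant medication on the initial IMP administration day will be calculated" (7.5), the deviation classes in 7.6 have no class for these permitted changes, and only listing PDATA-4.1 would show them.

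**The concern.** Both gaps concern what a counted response means. A child taken off tolvaptan for excessive aquaresis or a sodium rise (Protocol 3.8.3.1) may already have lost 1.7% of body weight and so count as a success of a treatment that could not be continued. A child whose diuretic is increased on, say, Day 3 may reach 1.7% partly or wholly because of the diuretic.

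The trial has one arm, so no comparison removes the second effect. The rationale in Protocol 3.5.1 relies on the urine condition to tie weight loss to tolvaptan. That works against vomiting or poor food intake. It does not work against another diuretic, which raises urine volume too.

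A reader who regards either event as failure has no planned estimate or interval. Comparing the two planned sets looks like a check but need not reveal the difference.

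**Working it through.** **Interval method.** The plan gives no figure for this point. Its sample sizes show which interval is meant. With Clopper-Pearson limits and the plan's threshold of 0.3:

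- N = 30 at a true rate of 0.6 needs 15 responders and gives probability 90.3%; N = 29 gives 86.4%.
- N = 68 at 0.5 needs 29 responders and gives 90.9%. N = 66 also passes (91.2%) but N = 67 does not (88.9%), so 68 is the smallest size from which the probability stays at 90% or more.

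Both stated sizes are reproduced, so the same interval is used below.

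**Can the two planned rates hide the effect?** Take 60 children in the FAS, 30 scored as responders, and 4 who stop early without 3 days at any one dose, 2 of them scored as responders. These counts are illustrative.

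| Analysis | Rate | Exact 95% CI |
|---|---|---|
| FAS, carry-forward | 30/60 = 50.0% | 36.8 to 63.2 |
| Dose maintenance set | (30 − 2)/(60 − 4) = 28/56 = 50.0% | 36.3 to 63.7 |
| FAS, stoppers as non-responders | (30 − 2)/60 = 28/60 = 46.7% | 33.7 to 60.0 |

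Whenever stoppers respond at the same rate as the rest, the first two agree and the third is lower.

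**Size for early stoppers.** One child is 1/60 = 1.7 points. If stopping is unrelated to response, the fall is d × p, with d the share stopping before 3 days at the evaluation dose and p the counted response rate (0.5 to 0.6 in SAP 4). The documents give no paediatric d. The adult dose-ranging trial (Protocol 1.2.1) gives adverse-event stops over 7 days:

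| Adult group | Stops | d | Fall at p = 0.5 | Fall at p = 0.6 |
|---|---|---|---|---|
| 15 mg | 0/28 | 0% | 0 points | 0 points |
| 30 mg | 2/33 | 6.1% | 3.0 | 3.6 |
| 45 mg | 5/28 | 17.9% | 8.9 | 10.7 |
| Placebo | 3/29 | 10.3% | 5.2 | 6.2 |

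This is a rough guide only. The timing of those stops is not given, stops after the 3-day assessment would not be reclassified, and this protocol also stops treatment on sodium, potassium and liver thresholds.

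**Room for an added drug.** Without dose reduction, the evaluation dose starts on Day 1, 3, 5 or 7 for 0.05, 0.15, 0.3 or 0.5 mg/kg/day (Protocol 3.2.2), and the endpoint weight falls 3 days later, on Day 4, 6, 8 or 10. Subtracting the 24 hours after the first dose (to Day 2) leaves 2, 4, 6 or 8 days for a permitted change. This is opportunity, not frequency, but it is longest at the highest dose, which matters for the by-dose rates. In a 10 kg child the target is 0.017 × 10 = 0.17 kg.

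**Which 3 days?** Suppose a child receives 0.05, 0.05, 0.15 (sufficient urine), is reduced to 0.05 and stops after one day. SAP 5.7 applies: "If the dose was reduced without having been administered for 3 days, then the reduced dose". The evaluation dose is 0.05. The child has 3 days in total at 0.05 but one since the reduction. Neither SAP 5.2 nor Protocol 3.10 (completers are "Subjects who have received IMP administration at evaluation dose" for 3 days) says whether the days must be consecutive or after the reduction.

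**Urine window for discontinuers.** Protocol 3.5.1 gives an end point but no start point; Protocol 7.3 and SAP 5.6 and 6.1 use the evaluation-dose period. With assumed values of 500 mL at baseline, 450 and 450 mL at 0.05, 560 mL at 0.15, then stop, the mean from the first dose is 1,460/3 = 487 mL (fails) and at the evaluation dose 560 mL (passes). SAP 14 does not list the SAP 6.1 rewording.

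**The case against.** Carry-forward is a prespecified rule, and a weight is scheduled at discontinuation (Protocol 3.7.1.6), so the value used will often be a measured one. It can also understate the 3-day effect, since a child who stops early with little loss is a non-responder anyway. Excessive aquaresis is the drug's own action, so scoring it as failure mixes tolerability with efficacy. Discontinuations are reported by reason and in the adverse event tables. All of this stands, and it is why the primary analysis should not change.

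On added drugs, eligibility requires that more diuretic is not expected to work or is difficult to give (Protocol 3.3), changes are barred in principle, and the conventional diuretic dose should not be changed when tolvaptan is reduced (Protocol 3.2.3). Increases are therefore less likely, but not excluded. Changes made for safety may also be reductions, which would bias against response.

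A reader might infer that the primary rate is biased upwards, or that reclassifying a few children would overturn a positive trial. The documents support neither. The direction for stoppers is not fixed, and the 0.3 threshold is a sample-size input, not a stated success rule, so no comparison with it is made here. Nor is the child in the dose-reduction example shown to be wrongly kept in the dose maintenance set; the text leaves that open.

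**Conclusion.** The gap is real and modest. A stopper with a weight after evaluation-dose treatment can be scored as a responder, and no efficacy rule in the SAP handles a permitted start or increase of a diuretic or injectable heart-failure drug. The second efficacy set answers neither question: it leaves out children without 3 days at one dose and keeps children with increases.

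The added-drug part is the stronger, because without a control arm neither the design nor the urine condition separates the two effects. Its frequency is unknown. For stoppers, the adult rates give a fall of 0 to about 11 points, assuming that stopping is unrelated to response and that every adult stop would have come before the 3-day assessment. The true figure could lie outside that range, because paediatric stopping is unknown and may be linked to response.

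This is a worthwhile improvement rather than a flaw in the primary analysis. The urine window and the missing SAP 14 entry are wording points likely to affect few children.

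**What to change.** Keep the primary analysis. Add to SAP 8.1.1 a supplementary analysis in the FAS giving the number, percentage and exact 95% CI of responders, counting as non-responders children who:

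- (a) stop before completing 3 days at the evaluation dose; or
- (b) have a diuretic or injectable heart-failure drug started or increased after the pretreatment observation period and before the endpoint weight. An increase dated the same day as that pre-breakfast weight counts as after it unless a recorded time shows otherwise.

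Show the number reclassified under (a) and (b) separately, and list the number of children with reductions.

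State once, for Protocol 3.10, SAP 5.2 and this analysis, whether the 3 days must be consecutive and after any dose reduction. Align the discontinuer urine window in Protocol 3.5.1 with the evaluation-dose period, and list the SAP 6.1 rewording in SAP 14.

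The cost is one table and a few clauses. Dosing days and the reason and details of drug changes are already recorded. The downside is that the supporting rate may be less favourable and mixes tolerability with efficacy, which is why the counts are shown by reason.

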## **5.7 Definition of Evaluation Dose**

Of the doses administered as specified in [Section 3.2.2](#) and [Section 3.2.3](#), the dose meeting the following criteria is defined as an evaluation dose.

- 1) If sufficient increase in urine volume was obtained during the course of dose escalation, or if the dose was increased to 0.5 mg/kg/day because sufficient increase in urine volume was not obtained:
  - If the dose was not subsequently reduced, then that dose
  - If the dose was reduced without having been administered for 3 days, then the reduced dose
  - If the dose was reduced after having been administered for 3 days, then the dose before reduction

- 2) If IMP administration was discontinued before sufficient increase in urine volume was obtained during the course of dose increase:
  - The dose at final IMP administration

## **6 Primary and Secondary Outcome Variables:**

### **6.1 Primary Outcome Variables**

The percentage of subjects who satisfy the following condition:

- Body weight on the day after the third day of treatment with tolvaptan at the evaluation dose (see [Section 7.4](#)) is decreased by 1.7% or more from the weight measured before breakfast on the first day of the treatment period

However, mean daily urine volume for the 3 days of treatment with tolvaptan at the evaluation dose must be higher than the daily urine volume for the pretreatment observation period. For subjects whose treatment period at evaluation dose is less than 3 days, mean daily urine volume at the time of the treatment at evaluation dose must be higher than the daily urine volume for the pretreatment observation period.

### **6.2 Secondary Outcome Variables**

- Body weight
- Edematous symptoms (edema [lower limbs, eyelids, etc], dyspnea, jugular venous distension, pulmonary congestion, cardiothoracic ratio, respiration rate at rest, pulse rate, and pleural effusion), central venous pressure (only subjects with central venous catheterization), and retention of pericardial effusion (only subjects requiring echocardiography to confirm retention of pericardial effusion prior to tolvaptan administration)
- Daily urine volume

## **7 Disposition and Demographic Analysis**

### **7.1 Subject Disposition**

In the subjects who provided informed consent (screened subjects), the number of subjects who provided informed consent and received IMP administration, as well as the number and percentage (the denominator is the number of subjects treated with IMP administration) of completed subjects after IMP administration and discontinued subjects after IMP administration will be presented. The number and percentage of discontinued subjects after IMP administration will be presented by reason for discontinuation. The

number and percentage of subjects receiving extended treatment and those receiving a reduced dose will be presented.

The number and percentage of subjects included in and excluded from each analysis set in those treated with the IMP will be presented.

## 7.2 Demographic and Baseline Characteristics

For the full analysis set and safety analysis set, each variable will be calculated based on **Table 7.2-1**.

Table 7.2-1 Demographic and Baseline Characteristics			
Variable	Time point	Method	Level
Age (years)	At the time of informed consent	Descriptive statistics	-
		Frequency distribution	6 months to less than 2 years, 2 years to less than 7 years, 7 years to less than 15 years
Gender	-	Frequency distribution	Female, Male, Undifferentiated
Height (cm)	Screening	Descriptive statistics	-
Body weight (kg)	Screening	Descriptive statistics	-
BMI (kg/m  ) a	Screening	Descriptive statistics	-
Race	-	Frequency distribution	American Indian or Alaska Native, Asian, Black or African American, Native Hawaiian or Other Pacific Islander, White, Other
Presence/absence of complications	Screening	Frequency distribution	Yes, No
Presence/absence of a medical history	Screening	Frequency distribution	Yes, No
Presence/absence of a history of surgery	Screening	Frequency distribution	Yes, No

aBMI = body weight (kg)/(height [m] × height [m])

## 7.3 Baseline Disease Evaluation

For the full analysis set and safety analysis set, each variable at baseline will be calculated.

Table 7.3-1                    Baseline Disease Evaluation		
Variable	Method	Level
Edema • Lower limbs	Frequency distribution	None, Mild, Moderate, Severe
Edema • Eyelids	Frequency distribution	Present, Absent
Dyspnea	Frequency distribution	Present, Absent
Jugular venous distension	Frequency distribution	Present, Absent
Respiration rate at rest (times/minute)	Descriptive statistics	-
Pulse rate (times/minute)	Descriptive statistics	-
Pulmonary congestion	Frequency distribution	None, Mild, Moderate, Severe
Cardiothoracic ratio (%)	Descriptive statistics	-
Pleural effusion	Frequency distribution	Present, Absent

## 7.4            Treatment Compliance

For the full analysis set and safety analysis set, the frequency distributions for the presence/absence of days on which the IMP is not administered from the first day of the treatment period to the completion or discontinuation of the IMP administration will be calculated.

